16.66 Patient's Perception of Cosmesis

All eligible patients who have undergone surgery that was not converted to a mastectomy will be included in these analyses.

Patient's perception of cosmesis will be assessed at their initial post-operative visit as well as 1, 6, 12, and 24 months following completion of WBI using the BREAST-Q® subscales: satisfaction with breasts, satisfaction with overall outcome, and physical well-being.

Patients registered after surgery will not partake in the pre-operative assessment but will be asked to complete subsequent cosmesis surveys.

The following statistical analyses will be conducted separately for those women who undergo an ALND and those who do not undergo an ALND.

16.661 At Each Time Point

The total score for each of these subscales will be determined using the BREAST-Q® scoring module

For each of the subscales, a 95 % binomial confidence interval for the proportion of patients reporting deficits in that domain will be constructed. Also, a 95 % binomial confidence interval for the proportion of patients indicating that their cosmesis result on the one item questionnaire was poor or fair (scores: 3 or 4) will be constructed. For each of the three subscales, a Wilcoxon rank sum test will be used

to assess domain score differs between those women reporting a poor/fair cosmesis result on the one item questionnaire (scores 1 or 2) and those women reporting a good/excellent cosmesis result on the one item questionnaire.

16.662 Across Time

At years 1 and 2 post WBI, logistic regression modeling will be used to assess which patients, disease, and/or treatment characteristics as well as of breast lymphedema are associated with an increased likelihood of each of the following endpoint: reporting a poor to fair cosmesis, poor satisfaction with breast cosmesis, poor satisfaction with overall outcome, and poor physical well-being.

The agreement between year 1 post WBI cosmesis findings and year 2 post WBI cosmesis findings in terms of a poor to fair cosmesis, poor satisfaction with breast cosmesis, poor satisfaction with overall outcome, and poor physical well-being will be assessed using McNemar tests.

16.663 Agreement with Surgeon's Perception of Cosmetic Results at Initial Post-surgical Evaluation

Impression of cosmesis will be dichotomized as poor to fair versus good to excellent. A 95 % confidence interval will be constructed for the proportion of cases where the patient and his surgeon agree in terms of cosmesis results.

16.664 Differences of the Extent of Disease Described on Mammography Compared with Surgical Findings

All eligible patients who have initiated surgery will be included in the analysis of this endpoint. The maximum lesion dimension and location of each lesion found on mammogram will be determined on central review. Agreement between the lesion size on mammogram and the lesion size reported on surgical pathology report will be examined using the approaches proposed by Bland and Altman. That is, a plot of the average of lesion size on mammogram and the lesion size reported on surgical pathology report versus the difference in lesion size between that found on mammogram and that found on surgery will be constructed to examine systematic biases. A 95 % z-confidence of the difference in lesion size between that found on mammogram and that found on surgery will be constructed. Percent agreement will be used to assess the extent of agreement between location of the lesion seen on mammogram and the location of the lesion reported on surgical pathology report.

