1.24 Cosmesis

1.241 4-point Scoring System of Breast Cosmesis (Winchester and Cox, 1992) A single item question will be administered asking both the patient and her surgeon to assess the overall cosmetic result (excellent, good, fair, and poor) (Olivotto *et al.*, 1989; Winchester and Cox, 1992). This questionnaire is also being used in the trial NSABP B-39. Olivotto *et al.* also used this single item questionnaire to assess technical factors impacting whether a patient considered the cosmesis a failure following BCT. In general, patients with a fair or poor score are considered to be a cosmetic “failure”. Olivotto *et al.* demonstrated that cosmetic scores for patients classified as excellent or good cosmetic score remained consistent after 3, 5, and 7 years in 88 %, 90%, and 78 % of the patients, respectively.

1.242 BREAST-Q®

The BREAST-Q®, a patient-reported outcome (PRO) instrument for breast surgery patients, was recently developed to address the lack of instruments to measure outcome in the breast surgical population (Pusic *et al.*, 2009). The questionnaire was developed with strict adherence to guidelines recommended by the Scientific Advisory Committee of the Medical Outcomes Trust and the US Food and Drug Administration (Lohr, 2002; USDHHS, FDA, CDER, CBER and CDRH (2009)). This process included development of a conceptual framework, item generation, scale formation with item reduction, and psychometric evaluation. At present, the BREAST-Q® contains three modules (post mastectomy reconstruction, breast reduction and breast augmentation), each with a preoperative and postoperative version. Each module includes six independent scales (satisfaction with breasts, satisfaction with overall outcome, psychosocial well-being, sexual well-being, physical well-being and satisfaction with care). Psychometric evaluation

suggests that it exceeds criteria for rigorous measurement as established by quality of life researchers and government regulatory bodies internationally. More specifically, each scale fulfilled both Rasch and traditional psychometric criteria (including person separation index 0.76 to 0.95; Cronbach's alpha 0.81 to 0.96; and test-retest reproducibility 0.73 to 0.96). The Breast Q was developed using patient interviews, focus groups, expert panels, and a literature review to develop a conceptual framework and a list of questionnaire items.

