2.2 Secondary Clinical Goals

2.21 Conversion Rate to Mastectomy

To examine the conversion rate to mastectomy secondary to persistent positive margins; poor cosmesis within the first year of attempting breast conservation surgery (BCS) or inability to satisfy the radiation dose constraints on the boost to the lumpectomy bed of each site of disease.

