2.23 Patient's Perception of Cosmesis

To assess patient's perception of cosmesis and incidence of breast lymphedema.

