13.2 Conditions Requiring Study Termination

Patients who convert to a mastectomy for any reason within a year of initial surgery will go to the observation phase of the study. All data and forms prior to and up to mastectomy must be submitted. Tissue from the mastectomy should be submitted if possible. Patients will be followed for survival yearly for 5 years after treatment discontinuation.

Patients found to have any of the following:

- those with persistent positive margins who decline mastectomy;
- the dose constraint is not met (≤ 10 weeks of initial attempt of WBI planning in patients not receiving adjuvant chemotherapy, or ≤ 8 weeks after completion of chemotherapy for those patients receiving chemotherapy)

will have participation in the study terminated. The on-study material, surgery forms, pathology forms and the End of Active Treatment/Cancel Notification Form must be submitted. No further data submission is needed.

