16.62 Conversion to Mastectomy

The conversion rate to mastectomy secondary to persistent positive margins; poor cosmesis within the first year of attempting BCS; or inability to satisfy the radiation dose constraints on the boost to the lumpectomy bed of each site of disease

All eligible patients who have initiated surgery will be included in the analysis of conversion to mastectomy. A 95 % binomial confidence interval will be constructed for the percentage of patients who converted to mastectomy. Logistic regression analysis will be used to assess whether the likelihood of conversion to mastectomy differed with respect to patient and/or disease characteristics.

An interim efficacy analysis will not be performed; final analysis will be performed at year 7 after patients have at least 5 years of follow-up.

Patients enrolled subsequent to surgery will be excluded from this analysis.

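### Section 16.66 drops every woman converted to mastectomy from the cosmesis analyses, including conversions for poor cosmesis, so membership of the cosmesis set depends partly on the outcome

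*Combined protocol and SAP*

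**What the plan says.** The secondary goal in Section 2.23 reads "To assess patient's perception of cosmesis and incidence of breast lymphedema". Section 16.661 analyses it at each time point through "a 95 % binomial confidence interval for the proportion of patients indicating that their cosmesis result on the one item questionnaire was poor or fair", alongside the BREAST-Q subscales. Section 1.241 explains that, in general, "patients with a fair or poor score are considered to be a cosmetic" failure.

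The population for all of this is fixed at the head of Section 16.66: "All eligible patients who have undergone surgery that was not converted to a mastectomy will be included in these analyses". The analyses under that heading include the year 1 and year 2 models (16.662) and the patient-surgeon agreement at the initial visit (16.663).

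Conversion is a separate secondary goal. Section 2.21 lists its reasons as persistent positive margins, then "poor cosmesis within the first year of attempting breast conservation surgery (BCS) or inability to satisfy the radiation dose constraints" on the boost. Sections 16.2 and 16.62 repeat the three reasons. Section 16.62 gives the denominator: "All eligible patients who have initiated surgery will be included in the analysis of conversion to mastectomy". It then removes women enrolled after surgery.

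For women who convert within a year of initial surgery, Section 13.2 states: "All data and forms prior to and up to mastectomy must be submitted". After that they are followed yearly for survival.

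**The concern.** The plan accepts that some women will lose the breast because it looks poor, and it then measures how the breast looks only in women who kept it. Whether a woman belongs to the cosmesis set is settled by something that happens after some of her ratings were given, and that event can be caused by the quantity being rated. This is selection on the outcome.

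Two things follow. Valid early ratings are thrown away. In addition, the fair/poor proportion describes retained breasts, while the goal is likely to be read as describing what women can expect cosmetically when conservation is attempted for two or three foci. A reader who sees only the cosmesis table would get a more favourable answer to that second question than the trial's own data support.

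**Working it through.** **The plan's own figure.** The plan gives no expected fair/poor rate, no expected number of conversions for cosmesis and no precision statement for the cosmesis goal. The only interval stated for conversion is in Section 16.51: 35 of 100 gives a lower 95% bound of 25.7%. The exact binomial lower limit is the 2.5% quantile of Beta(35, 66) = 25.73%, so the figure reproduces. It does not bear on the cosmesis population.

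**Which ratings are lost.**

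- *Before surgery:* none. The baseline booklet (Appendix II) holds only the two LASA items.
- *Initial post-operative visit:* the first cosmesis booklet is due 5 to 30 days after final surgery (Sections 4.1 and 7.4). A woman who reaches this visit with her breast and converts later has a valid rating, and usually a paired surgeon rating. Section 16.66 removes both, so 16.663 is affected too.
- *6 months after WBI:* without chemotherapy, Section 7.63 has WBI starting no later than 10 weeks after surgery, or 12 weeks after a re-scan. Section 4.1 gives its length as about 6 weeks. The visit then falls at about 10 + 6 + 26 = 42 to 12 + 6 + 26 = 44 weeks after the last operation. It can therefore precede a conversion made within the first year.
- *Years 1 and 2 after WBI:* a conversion within one year of initial surgery, as in Section 13.2, comes before the year 1 visit, because that year starts only when WBI ends. No observed rating is lost here.

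**Where the conversions are counted.**

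| Woman converted for poor cosmesis | In 16.62 (conversion) | In 16.66 (cosmesis) |
|---|---|---|
| Registered before surgery | Yes, pooled with margins and dose constraint | No |
| Registered after surgery | No | No |

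**Size if conversions for cosmesis count as failures.** Let N be the women retained, x those rated fair/poor and c the conversions for poor cosmesis.

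- Planned estimate: x/N
- Estimate counting conversions: (x + c)/(N + c)
- Difference: c(N − x) / [N(N + c)], which is positive whenever c > 0 and x < N

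Assumptions: N = 200, borrowed from the evaluable target for the primary endpoint in Section 16.3; fair/poor 10% or 20%; c from 3 to 10. The documents give none of these for cosmesis.

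| Planned | c = 3 | c = 10 |
|---|---|---|
| 20/200 = 10.0% | 23/203 = 11.3% (+1.3) | 30/210 = 14.3% (+4.3) |
| 40/200 = 20.0% | 43/203 = 21.2% (+1.2) | 50/210 = 23.8% (+3.8) |

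Over a wider assumed range (c from 2 to 20, fair/poor 10% to 30%), the difference runs from 0.7 points (60/200 to 62/202 = 30.7%) to 8.2 points (20/200 to 40/220 = 18.2%). Section 16.66 also splits every analysis by axillary dissection, so a stratum can move more. For instance, 6/60 = 10% becomes 11/65 = 16.9% with five conversions, all figures assumed.

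**The case against.** The best defence is that the plan has two secondary endpoints that together tell the story: conversion, with its own interval and logistic regression, and cosmesis in breasts that were kept. The restriction is openly pre-specified, and it suits the instruments. The one-item scale asks how the treated breast looks now, and the BREAST-Q module asks about the lumpectomy breast. Neither makes sense after mastectomy, so a retained-breast analysis is legitimate. This stands, and it limits the point. It does not explain why ratings given before conversion are dropped. Nor does the conversion endpoint fully compensate, since no breakdown by reason is planned and women registered after surgery are left out.

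Several stronger readings are tempting, and the documents do not support them:

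- *The year 1 and year 2 models discard observed failures.* They do not, for conversions within one year of initial surgery. Those models change only if conversion is itself counted as fair/poor.
- *A cosmesis booklet exists for every converted woman.* Section 13.2 requires forms up to mastectomy, but it cannot produce a booklet not yet due. If mastectomy is the final operation, there may be none.
- *The fair/poor proportion is biased downward at every visit.* This is certain only when conversions count as failures. For observed ratings the net direction is unknown: a woman later converted for cosmesis may not yet have rated fair/poor, and women converted for margins or dose constraint may have rated well.
- *The women removed have the worst results.* This is a natural inference, but the documents do not say whose judgement leads to conversion.

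**Conclusion.** The point holds in a limited form. Section 16.66 makes the cosmesis set depend partly on the outcome, discards valid ratings made before conversion and leaves some conversions for poor cosmesis uncounted anywhere. If these conversions are regarded as cosmetic failures, the retained-breast proportion understates failure after attempted conservation.

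The size is unknown. About 1 to 4 percentage points is an illustration that rests on 200 retained women, 10-20% fair/poor and 3-10 such conversions. Even its upper values lie inside the sampling intervals of the planned estimates: 14.3% against 6.2-15.0% for 20/200, and 23.8% against 14.7-26.2% for 40/200. The shift is nevertheless systematic and in one direction.

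A reader might infer that a composite should replace the main analysis. That is a choice of estimand on which statisticians may differ, and nothing in the documents requires it. This is an inexpensive improvement to a secondary analysis and leaves the primary endpoint untouched.

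**What to change.** Revise Section 16.66 as follows.

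1. At each visit, include all eligible women who had breast-conserving surgery and completed a cosmesis booklet before any mastectomy. Apply this to 16.663 as well.
2. Keep the retained-breast analysis at the year 1 and year 2 visits and label it as such. Add a pre-specified sensitivity analysis of the one-item fair/poor endpoint (16.661 and 16.662) that counts conversion for poor cosmesis as fair/poor from conversion onward. BREAST-Q scores stay restricted to retained breasts after conversion.
3. Report the number of conversions for poor cosmesis beside the cosmesis results, including women registered after surgery.

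The section should also say whether converted means within one year of initial surgery, as in Section 13.2, or at any time.

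The cost is SAP wording and one extra table. The early ratings are on forms that Section 13.2 already requires, and patient care does not change. The downside is that the sensitivity endpoint is a composite after conversion, and the cosmetic result may look slightly less favourable.

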In this study, we will use the independent scales for satisfaction with breasts and satisfaction with overall outcome from the Breast Q[©] BCT module. Although the final version of the BCT module is still being finalized, the individual questions will not change and no questions will be added, therefore using these questions will enable calculation of a score once the Breast Q[©] BCT scoring is complete.

1.243 Breast Lymphedema (BLE) Symptom Survey (Degnim *et al.*, 2008).

Lymphedema in the ipsilateral arm is a well-recognized complication following breast/axillary surgery, but can also occur in the breast after surgery. We have previously evaluated clinical and surgical factors associated with the development of postoperative breast lymphedema (BLE); yet, BLE diagnosis is currently non-standardized and is based on clinical impression.

Previously, we prospectively evaluated patients undergoing non-mastectomy procedures for signs and symptoms of lymphedema in the operated breast. BLE diagnosis was based on a graded physical exam targeting clinical signs of diffuse skin edema, erythema, and their location. Diagnosis was independent of patient reported symptoms. Additionally, patients also rated symptoms in their operated breast for heaviness, discomfort, redness, visible swelling and associated degree of distress using a 10-point scale (“not at all” = 0 to “a lot” = 10). In subjects with clinical BLE, skin edema and breast erythema were observed in 26/26 (100 %) and 13/26 (50 %), respectively, compared to 5/38 (13 %) and 4/38 (11 %) without clinical BLE, respectively. BLE was observed in more than one quadrant for the majority of patients with BLE (skin edema 18/26 = 69 %, and erythema 10/13 = 77 %). Additionally, BLE patients had significantly higher scores for breast heaviness, discomfort, redness, and swelling and distress associated with these symptoms was significantly elevated only for symptoms of breast heaviness (mean 3.4 vs. 1.0, $p = 0.01$) and discomfort (mean 2.9 vs. 1.4, $p = 0.03$).

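### BREAST-Q scores are reduced to undefined deficit and poor categories for the estimates and models; the score itself should be the main outcome

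*Combined protocol and SAP*

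**What the plan says.** Patient-perceived cosmesis is a secondary goal (Section 2.23) and a listed secondary endpoint (Section 16.2). Section 16.66 analyses three BREAST-Q subscales: breast satisfaction, satisfaction with the overall outcome, and physical well-being.

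- **Scoring (16.661):** "The total score for each of these subscales will be determined using the BREAST-Q® scoring module".
- **Estimates at each visit (16.661):** for each subscale, "a 95 % binomial confidence interval for the proportion of patients reporting deficits in that domain will be constructed".
- **Models at years 1 and 2 after whole breast irradiation (16.662):** the binary outcomes in the logistic regressions, and again in the McNemar tests, include "poor satisfaction with breast cosmesis, poor satisfaction with overall outcome, and poor physical well-being".
- **Full score (16.661):** "For each of the three subscales, a Wilcoxon rank sum test will be used" to compare domain scores between women with poor/fair and good/excellent results on the one-item cosmesis question.
- **Split (16.66):** "The following statistical analyses will be conducted separately for those women who undergo an ALND" and for those who do not. No pooled or ALND-adjusted analysis is described.
- **State of the instrument (1.242):** "Although the final version of the BCT module is still being finalized, the individual questions will not change and no questions will be added". The section expects a score to be calculable once scoring of this module is complete.

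**The concern.** The plan obtains a graded score for each scale and then replaces it with a yes/no outcome for both the reported estimates and the regressions, without saying where the line falls. The reported percentage with a deficit is set directly by that line. The trial has a single arm and the scores arrive over years of follow-up, so nothing in the plan prevents the line being chosen once the data can be seen. Apart from that, a yes/no version of a score carries less information about which patient, disease or treatment factors go with a worse result, and that is the question Section 16.662 asks.

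At stake are the interpretability of the main patient-reported results and the precision of the search for predictors.

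**Working it through.** **Step 1. Is a threshold defined anywhere?**

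- Sections 16.661 and 16.662 give no cut-off for deficit or for poor, and do not say whether the two terms mean the same thing. The scoring module is cited only as the source of the total.
- Deficit cannot mean a fall from a pre-operative BREAST-Q score. The baseline booklet (Appendix II) holds two LASA items only; BREAST-Q appears only in the post-operative booklet (Appendix IV).
- Other outcomes do have rules. Section 16.65 defines breast lymphedema by a symptom score above 0 plus edema on examination, and Section 1.241 treats fair or poor on the one-item scale as a cosmetic failure.
- The one-item rule is inconsistent within 16.661: poor/fair is coded 3 or 4 in one sentence and 1 or 2 in the Wilcoxon sentence. The descriptions in Appendix IV run from minimal change at 1 to marked change at 4, which agrees with 3 or 4.

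**Step 2. The plan's own figures.** Section 16.66 states no sample size, power or threshold, so there is none to reproduce there. The working number is about 200 women, from Section 16.3. That section's sizing does reproduce: the exact two-sided Poisson upper limit for 8 events is 31.53/(2 × 200) = 7.88%, below 8%.

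**Step 3. Cost of dichotomising in the association analyses.** Assume a roughly normal score, with a proportion p called poor. Efficiency relative to the full score is φ(z_p)² / [p(1 − p)], where φ is the normal density and z_p the p-quantile.

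| Called poor (assumed) | Efficiency | Information lost | 200 women act like |
|---|---|---|---|
| 50% | 0.637 | 36% | 127 |
| 30% | 0.576 | 42% | 115 |
| 20% | 0.490 | 51% | 98 |
| 10% | 0.342 | 66% | 68 |
| 5% | 0.224 | 78% | 45 |

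The finite-sample check is a comparison of two groups of 100 differing by 0.4 SD (assumed). Power on the score is 80.7%. After cutting at 50%, 30%, 20% and 10% it is 61.2%, 56.8%, 50.0% and 37.0%. The size needed per group rises from 99 to 155, 173, 204 and 295. The implied losses, such as 1 − 99/155 = 36% and 1 − 99/295 = 66%, match the table.

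The Wilcoxon test already planned keeps 3/π = 95% efficiency under normality, so the loss comes from the cut and not from using a rank method.

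**Step 4. The ALND split, taken separately.** Splitting leaves the total information unchanged but widens the intervals within each stratum. For a 20% proportion, the exact 95% interval has a half-width of 5.8 points at n = 200, 8.3 at n = 100, 10.8 at n = 60 and 13.3 at n = 40. The documents do not give the ALND share; Section 7.2 leaves completion dissection with one or two positive sentinel nodes to the surgeon.

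**The case against.** Several counter-arguments have force.

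- **The proportion with a deficit is a legitimate estimand.** This stands. The efficiency formula compares ways of estimating an association and says nothing against a descriptive percentage. Against the 16.661 proportions, the only complaint is the missing threshold.
- **The full score is used.** This stands in part. The Wilcoxon test keeps it, but only compares scores between one-item groups. It neither estimates the level of a score with an interval nor identifies predictors.
- **The scoring module may supply thresholds.** That source cannot be seen from here. A reader might infer that no cut-off exists, or that one would certainly be picked after the data are known. The documents show only that the plan neither specifies a cut-off nor cites one.
- **The ALND split is defensible.** This stands. The BREAST-Q items in Appendix IV include shoulder and arm pain, difficulty lifting the arms and arm swelling, which axillary surgery could plausibly affect. The split is therefore no reason to remove the stratified results.

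Two stronger readings are tempting. One is that the split itself discards a third to two-thirds of the information; Step 4 shows that it does not. The other is that regressions in the ALND group could not be fitted reliably. With 25–35% having ALND and 15% reporting a poor result, both assumed, there would be 200 × 0.25 × 0.15 = 7.5 to 200 × 0.35 × 0.15 = 10.5 events. With 80% ALND there would be 24 in that group and 40 × 0.15 = 6 in the other. The documents give neither rate and no number of covariates, so sparse data are a risk and not an established failure.

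**Conclusion.** The point holds within limits. Section 16.66 rests its BREAST-Q estimates, logistic regressions and McNemar tests on categories that the documents do not define, although a score will be available. In the association analyses, the information lost by modelling poor instead of the score is about 36%, 51% or 66% when 50%, 20% or 10% of women are called poor. These figures assume a roughly normal score, and the prevalences are illustrative because the documents give none.

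The ALND split is a separate and smaller matter: it costs precision within strata by an amount that depends on an unstated share, and it justifies only adding a pooled analysis. The endpoint is secondary and has no power statement, and the primary endpoint is unaffected. The change is worth making because it needs no new data.

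**What to change.** - **16.661:** report the mean or median of each subscale with a 95% confidence interval at each visit.
- **16.662:** make the score the outcome, in a linear model or a mixed model over the collected visits, pooled across ALND groups with ALND as a covariate. An ALND-by-visit term can be added if a different course over time is of interest. Keep the ALND-specific summaries as supportive. The year 1 to year 2 comparison then becomes a within-woman change in score.
- **Threshold:** if percentages with a deficit or a poor result are still wanted, fix and justify the cut-off, or cite its source, before analysis, and say whether the two terms coincide.
- **One-item scale:** reconcile the two codings of poor/fair in 16.661.
- **Visits:** align the list in 16.66 with the questionnaire schedule. The visit 1 month after irradiation does not appear in Section 4.1 (footnote 9), Section 4.2 (footnote 4) or Section 7.4, and those sections collect booklets yearly out to year 5.

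The cost is SAP wording only. The downside is that results are expressed in score points, which are less immediate to clinicians than a percentage.
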